5.7 APPROPRIATENESS OF MEASUREMENTS

The measurements performed during this trial are standard measurements in MDD treatment trials and will be performed in order to monitor safety aspects or assess treatment response in an appropriate way. Therefore, the appropriateness of all measurements applied in this trial is given.

6. INVESTIGATIONAL PLAN

In the event of force majeure or other disruptive circumstance (e.g. pandemic, war), the execution of the investigational plan as per this clinical trial protocol may not be feasible. With the consent of the participant, the sponsor and investigator may agree on alternative, back-up, or rescue methodology which may include, but will not be limited to, virtual trial participant visits and assessments, home healthcare nurse visits, direct-to-participant shipments of IMP, direct-from-participant shipments of IMP, or biological sample pick up from the participant's home. The implementation of these measures will depend on the participant's consent, operational feasibility, and local laws and regulations. Such alternative measures will be described in the participant information. If alternative methodology is implemented, the deviations from the original plan will be precisely documented.

6.1 VISIT SCHEDULE

The trial visit schedule is presented in the [SoA](#). Each visit date (with its window) is to be counted from Day 1 (day of randomisation/first intake of IMP, Visit 2). If a participant misses an appointment, it should be rescheduled, if possible. Subsequent visits should follow the original visit date schedule. The trial medication packs contain sufficient IMP to allow for the time windows described in the [SoA](#). Additional visits for the purposes of re-testing of laboratory parameters or AE monitoring may be included as deemed necessary by the investigator.

6.2 DETAILS OF TRIAL PROCEDURES AT SELECTED VISITS

Trial procedures and the order in which they are to be performed at each visit are listed in the [SoA](#). Additional details regarding visit procedures are provided below.

Clinical outcome assessments

The following requirements for the conduct of the clinician administered COAs (C-SSRS, MINI, HDRS-17, MADRS, and CGI-S) need to be followed:

- The site staff must be properly trained on all trial procedures and training documentation filed in the ISF. Qualification, training, and remediation (if needed) of the scales will be provided by a specialised vendor. The training standards and standards for the conduct of the assessments will be defined for each assessment individually and can be found in the ISF; it is the responsibility of the primary investigator at each site to ensure that all members of the site staff involved in the neuropsychological assessments undergo qualification and training by the vendor.
- Each assessment of the site-rater administered scales (C-SSRS, HDRS-17, MADRS, and CGI-S) should preferentially be done by the same members of the site staff for a given participant throughout the trial period.
- All MINI, HDRS-17, MADRS, and PCRS rater performed administrations will be audio recorded for central review by the vendor for quality assurance.
- During the neuropsychological testing, participants are allowed to take short breaks as needed, per the judgement of the rater/investigator.

The baseline/screening scale of the C-SSRS will be administered for eligibility confirmation

[REDACTED]. If there is an unscheduled visit due to suicidal ideation or behaviour, it is up to the investigator's judgement as to what appropriate testing should be completed as part of that evaluation.

Fasting

Participants should fast for 2 h prior to and 1 h after every IMP intake (both at the trial site and at home).

During Visits 2, 3, and 4, IMP intake should occur after all assessments are completed and the final dose of IMP should be taken on the day before the EoT Visit. Therefore, participants are not required to arrive to the trial site fasted for Visits 2, 3 and 4, however it should be ensured that the last meal was at least 2 h prior to IMP intake which will occur close to the end of the visit.

During Visit 5, participants should arrive to the trial site fasted as IMP intake will take place early during the visit to allow for pre and post-dose PK sampling. Participants should remain fasted until after the collection of the final PK sample during Visit 5 (2 h post IMP).

Safety laboratory and other laboratory tests

Trial participants do not have to be fasted for the blood sampling for safety laboratory tests. Participants should be asked about fasting/last meal. If the last meal was at least 10 h before the blood sampling, participants should be marked as fasted on the lab requisition form.

In rare cases where blood sampling for central laboratory is unable to be performed, safety laboratory analyses may be conducted at a local laboratory. The results and local lab standards of the laboratory tests must be transferred to the investigator who ensures medical review and documentation of any clinically relevant safety issue as an AE.

Ideally all parameters listed in [Table 6](#) and [Table 7](#) should be measured. If this is not feasible, the minimum required safety laboratory parameters are:

- Haematology
- Enzymes
- Substrates
- Electrolytes
- Urinalysis
- Pregnancy test
- Drug screening
- Infectious serology (only if clinical signs or symptoms are present)

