	
Main Exclusion Criteria:
 
• Have ever met diagnostic criteria for schizophrenia, schizoaffective disorder, schizophreniform disorder, bipolar disorder, or delusional disorder• Diagnosis with antisocial, paranoid, schizoid or schizotypal personality disorder, or MDD with psychotic features at the time of screening visit. Any other personality disorder that significantly affects current psychiatric status and likely to impact trial participation, as per the judgement of investigator• Diagnosis of any other mental disorder that was the primary focus of treatment within 6 months prior to screening, as per clinical discretion of the investigator• Treatment failure to 2 or more antidepressants in the current episode• A current or recent history of clinically significant suicidal ideation with intent within the past 3 months or a suicidal attempt within the past year• Participants with a body mass index (weight [kg]/height [m]²) lower than 18 kg/m² or greater than 40 kg/m² at screening• Diagnosis of a moderate to severe substance related disorder within 6 months prior to screening visit (with exception of caffeine and tobacco)• Frequent use of benzodiazepines• Positive drug screen (amphetamines, opiates, cocaine, barbiturates, phencyclidine) at screening. Participants with positive cannabis and benzodiazepine tests can be included if the investigator confirms that there is no moderate to severe substance related disorder or chronic benzodiazepine use• Have started psychotherapy or other non-drug therapies (e.g. acupuncture, hypnosis) within 3 months prior to screening or plan to start at any time during the study• Use of NMDA inhibitors (including ketamine/esketamine) for the current ongoing depressive episode or any past treatment failure with ketamine• Use of psychotropic medication (including antidepressant and antipsychotic therapy) which was not discontinued at least 5 half-lives prior to randomisation• Prior use of any investigational product within 6 months prior to randomisation• Have failed a 3rd party eligibility assessment within the 6 months prior screening• Known history of HIV infection and/or a positive result for an active Hepatitis B or C infection

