Haematology	Haematocrit Haemoglobin Red blood cells (RBC) Platelet count White blood cells (WBC) Mean corpuscular volume (MCV) Mean corpuscular haemoglobin (MCH) Mean corpuscular haemoglobin concentration (MCHC) Red cell distribution width (RDW) Reticulocyte Count
Automatic WBC differential (relative and absolute)	Neutrophils Eosinophils Basophils Monocytes Lymphocytes total
Manual differential WBC (if automatic differential WBC is abnormal)	Polymorphonuclear neutrophils (segs), band neutrophils (stabs), eosinophils, basophils, monocytes, lymphocytes
Coagulation	Prothrombin time (PT) Activated partial thromboplastin time (aPTT) International normalised ratio (INR)
Enzymes	Alanine aminotransferase (ALT, SGPT) Aspartate aminotransferase (AST, SGOT) Alkaline phosphatase (AP) Gamma-glutamyl transferase (GGT) Creatine kinase (CK) CK-MB, only if CK is elevated Lactic dehydrogenase (LDH)
Hormones	Thyroid stimulating hormone (TSH)
Substrates	Glucose Creatinine, enzymatic eGFR ¹ Urea nitrogen Total bilirubin (fractionated if increased) Total protein Albumin C-reactive protein (CRP) Globulin Albumin / globulin ratio Total cholesterol Triglycerides
Electrolytes	Sodium Potassium Chloride Phosphate Calcium

1 Estimated glomerular filtration rate (eGFR) will be calculated using Chronic Kidney Disease Epidemiology [CKD-EPI] equation for adults

Table 6 (cont'd) Safety laboratory tests

Functional laboratory group	Test name
Urinalysis (qualitative determination)	Urine nitrite Urine protein Urine glucose Urine ketone Urine bilirubin Urine haemoglobin (detects erythrocytes) Urine leukocyte esterase (detects leucocytes) Urine pH Specific gravity
Urine sediment (microscopic examination if erythrocytes, leukocytes, nitrite, or protein are abnormal in urine)	Only positive findings will be reported (e.g. presence of sediment bacteria, casts in sediment, squamous epithelial cells, erythrocytes, leukocytes)
Urine pregnancy test (only for female participants of childbearing potential)	β-human chorionic gonadotropin (β-HCG)
Serum pregnancy test (only if urine pregnancy test is positive)	β-HCG

Table 7 Exclusionary safety laboratory tests

Functional laboratory group	Test name

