5.2.6.1.4 Adverse events of special interest

The term “adverse event of special interest” (AESI) relates to any specific AE that has been identified at the project level as being of particular concern for prospective safety monitoring and safety assessment within this trial, e.g. the potential for AEs based on knowledge from other compounds in the same class. AESIs need to be reported to the sponsor’s Pharmacovigilance Department within the same timeframe that applies to SAEs; see Section [5.2.6.2.2](#).

The following is considered an AESI:

- Potential severe drug induced liver injury (DILI)

Potential severe DILI

A potential severe drug-induced liver injury (DILI) that requires follow-up is defined by any of the following alerts (alterations) of hepatic laboratory parameters that occur after the first dose of IMP:

1. AST or ALT elevation $\geq 3 \times \text{ULN}$ and total bilirubin $\geq 2 \times \text{ULN}$ measured at the same visit, or in samples drawn within 30 days of each other, OR
2. AST or ALT elevation $\geq 3 \times \text{ULN}$ and INR $\geq 1.5 \times \text{ULN}$ measured at the same visit, or in samples drawn within 30 days of each other, OR
3. AST or ALT elevation $\geq 3 \times \text{ULN}$ with new onset, or worsening of fatigue, nausea, vomiting, right upper quadrant pain or tenderness, fever, rash, and/or eosinophilia ($>5\%$), OR
4. AST or ALT elevation $\geq 5 \times \text{ULN}$

These laboratory findings constitute a hepatic injury alert, and participants showing any of these laboratory abnormalities need to be followed up according to the “DILI Checklist” provided in the ISF.

In case of clinical signs or symptoms of hepatic injury (icterus, unexplained encephalopathy, unexplained coagulopathy, right upper quadrant abdominal pain, etc.) without laboratory results (ALT, AST, total bilirubin) available, the investigator should make sure these

parameters are analysed, if necessary, in an unscheduled blood test. Should the results meet the criteria of hepatic injury alert, the procedures described in the DILI Checklist should be followed.

Additionally, with participants having a normal AST and ALT at baseline, the emergence of an isolated AST or ALT elevation between ≥ 3 -fold and $< 5 \times$ ULN requires repeat testing within 72 h. DILI Checklist is not required unless repeat testing triggers alerts 1, 2, 3, or 4.

The following events should lead to immediate discontinuation of trial IMP:

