- Hepatic injury alert numbers 1, 2, or 3
- Hepatic injury alert number 4, if persists > 2 weeks
- AST or ALT elevation $> 8 \times$ ULN

Following completion of the DILI Checklist, if the IMP cannot be excluded as a possible cause of the DILI event, discontinuation should be made permanent without rechallenge. If an alternate causality, e.g. acute viral hepatitis, is confirmed by the DILI Checklist evaluation, IMP may be re-started, if warranted.

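### The fallback local laboratory panel omits INR, so hepatic injury alert 2, a trigger for immediate discontinuation, cannot be assessed from that visit's sample

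*Protocol*

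**What the plan says.** Protocol Section 6.2 (safety laboratory paragraph) provides for failed central sampling: "In rare cases where blood sampling for central laboratory is unable to be performed, safety laboratory analyses may be conducted at a local laboratory". The full content of Tables 6 and 7 is the stated ideal. A shorter list follows, introduced by "If this is not feasible, the minimum required safety laboratory parameters are". It names haematology, enzymes, substrates, electrolytes, urinalysis, pregnancy test and drug screening, and ends with "Infectious serology (only if clinical signs or symptoms are present"). Coagulation is not on it. Table 6 (Section 5.2.3) has a separate Coagulation group, and INR appears nowhere else in that table.

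Section 5.2.6.1.4 makes potential severe drug-induced liver injury the only adverse event of special interest and defines four alerts. Alert 2 combines AST or ALT at or above 3 x ULN with INR at or above 1.5 x ULN, from one visit or from samples no more than 30 days apart. The events that should lead to immediate discontinuation include "Hepatic injury alert numbers 1, 2, or 3". An isolated AST or ALT rise of 3 to <5 x ULN in a participant with normal baseline values needs a repeat within 72 h, and "DILI Checklist is not required unless repeat testing triggers alerts 1, 2, 3, or 4".

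On serology, the synopsis excludes anyone with "a positive result for an active Hepatitis B or C infection". Section 5.2.3 says the investigator uses these results to judge eligibility, and Table 7 lists them among the exclusionary tests.

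**The concern.** A minimum safety panel should let the investigator apply the protocol's own stopping triggers. This one borrows Table 6 group names but drops the group that one trigger depends on. A site could follow Section 6.2 exactly and be unable to tell from that sample whether alert 2 is met. What is at stake is the timing of a safety stop for the trial's only adverse event of special interest, a risk for which the benefit-risk table (Section 1.4.2) names timely detection as the mitigation.

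A secondary mismatch concerns serology. The symptom condition carries no visit restriction, so at screening it sits badly with a test whose purpose is eligibility.

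**Working it through.** The plan gives no figure to reproduce, so the check sets the sections side by side. One piece of arithmetic, on visit spacing, follows.

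**Step 1. Which rules can the minimum panel support?** Table 6 places AST and ALT under Enzymes, total bilirubin under Substrates and INR under Coagulation.

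| Rule (Section 5.2.6.1.4) | Needs | From the minimum panel? |
|---|---|---|
| Alert 1 | AST/ALT, total bilirubin | Yes |
| Alert 2 | AST/ALT, INR | No, INR is absent |
| Alert 3 | AST/ALT plus a listed symptom or sign, or eosinophilia | Yes through symptoms; for eosinophils it depends on whether Haematology is read to include the differential, which is a separate group in Table 6 |
| Alert 4 and the >8 x ULN rule | AST/ALT | Yes |

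**Step 2. Who is affected?** A participant with raised INR, bilirubin below 2 x ULN and no alert 3 feature.
- AST/ALT 3 to <5 x ULN: no alert is visible from that sample. With normal baseline values the 72 h repeat applies. With abnormal baseline values no repeat rule is stated.
- AST/ALT 5 to 8 x ULN: alert 4 is met and the DILI Checklist starts, but alert 4 leads to discontinuation only if it persists beyond 2 weeks, whereas alert 2 would do so at once.
- AST/ALT above 8 x ULN: discontinuation follows without INR.

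**Step 3. Can another sample complete alert 2?** Safety laboratory target days (SAP Section 6.7, Table 5) are 1, 8, 15, 29, 43 and 51. The gaps are:
- 8 − 1 = 7
- 15 − 8 = 7
- 29 − 15 = 14
- 43 − 29 = 14
- 51 − 43 = 8

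All are below 30 days, so an INR from a neighbouring visit counts formally. An earlier INR meets the alert only if it was already raised. Otherwise a later one is needed. Day 1 sampling is before the first dose and the planned last dose is on Day 42 (Section 6.2.2.6), so a delayed stop matters for Days 8, 15 and 29. The waits to the next scheduled sample are 7, 14 and 14 days. After Day 29 that sample is Day 43, one day after the planned last dose.

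**Step 4. Do the other provisions supply INR?** The analytes of the 72 h repeat are not listed, and a repeat on the same minimum panel would again lack INR. The unscheduled test prompted by clinical signs of liver injury names ALT, AST and total bilirubin only.

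**Step 5. Serology.** Section 6.2 does not limit the symptom condition to visits after screening. Section 3.3.3 requires all exclusion criteria to be assessed at screening. Section 8.3.1 requires documented evidence before allocation and says that absent records do not make someone eligible. The texts disagree about what an asymptomatic person screened locally needs, but the latter two already stand in the way of randomisation without that evidence.

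**The case against.** The strongest reply is that this is a fallback within a fallback: central sampling must fail, which the protocol calls rare, and the full panel must then be infeasible locally. INR is part of the panel requested first. The 30-day pairing allows alert 2 to be completed from another sample. The repeat is to be judged against all four alerts, which presupposes that alert 2 can be assessed. Sections 6.1 and 6.2.2.1 allow extra visits for retesting at the investigator's discretion, and Section 6.2 requires medical review of local results. The laboratory manual and DILI Checklist, which may cover INR, are not among the documents.

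Most of this stands, and it rules out several stronger readings that a reader might infer:
- *That alert 2 can never be met when a local laboratory is used, or that its chance of detection is zero.* The limit applies only to the minimum panel and only to that sample.
- *That detection always waits up to 14 days.* That is the worst case, when no repeat or extra visit supplies an INR.
- *That an asymptomatic hepatitis carrier can be enrolled.* Sections 3.3.3, 5.2.3 and 8.3.1 largely prevent this.
- *That a later ALT rise in such a person could not be told apart from drug injury.* Section 5.2.6.1.4 expects the checklist to be able to confirm an alternative cause such as viral hepatitis.

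The reply does not remove the conflict between two stated rules. The minimum list names what is required, and what it requires is not enough to assess a trigger for immediate discontinuation. Retesting is discretionary or unspecified, and pairing with a later sample is slower than immediate.

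**Conclusion.** The point holds in a narrow form and is minor. When the local minimum panel is used, alert 2 cannot be assessed from that visit's sample. If nothing else supplies an INR, the delay is 7 to 14 days during treatment. If a 72 h repeat applies and includes INR, it is at most 72 h. These figures assume visits on target days and an INR at the next scheduled visit. The documents give no rate for local testing or for the infeasibility of the full panel, so the number of participants affected cannot be estimated. The serology condition is a smaller gap of wording that other sections largely cover. The primary analysis, sample size and type I error are not affected.

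**What to change.** Reconcile the minimum list in Section 6.2 with the alert definitions and discontinuation triggers in Section 5.2.6.1.4, so that the minimum panel covers every analyte those alerts use. The same reading should take in the 72 h repeat, whose analytes are not listed, and the unscheduled hepatic test, which does not name INR. Reconcile the serology condition with the hepatitis exclusion and Sections 5.2.3 and 8.3.1 by stating which visits it applies to. Alert thresholds and stopping rules stay as written, and the clinical content of the panel is for the sponsor to decide.

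The cost is a line or two in Section 6.2 and the laboratory manual, and a small amount of extra local testing in rare cases.

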6.2.1 Screening

No trial procedures should be done unless the participant has consented to taking part in the trial. After the participant has given informed consent in accordance with GCP and local legislation, the screening period will start with the first trial related procedure. The

participants should be recorded on the enrolment log. The participant should be registered in IRT as a screened participant.

At participating sites, participants will be invited to participate in data tokenisation (see Section [5.6.5](#)). A separate informed consent will be required for participation in data tokenisation.

Within the screening period, screening procedures may be extended to more than one physical visit if needed. Blood sampling, ECG, MINI, ATRQ, HDRS-17, CGI-S should be done at the beginning of the screening period. The first day of screening will be the starting point for the screening period calculation. The screening period (i.e. period between Visit 1 and Visit 2) should be kept as short as possible. If screening period needs to be extended, the Clinical Trial Leader or designee should be contacted to discuss further steps.

In addition, a short informational video intended to educate the participant about placebos and why they are used in clinical trials may be available for participants. The video advises the participant not to attempt to guess if they are on active drug or placebo, reminds them that there is always a chance they have been randomly assigned to placebo, and stresses the importance of reporting all symptoms, be they positive, negative, or neutral.

6.2.1.1 Rescreening of participants:

Rescreening of a participant can be done twice, if there is a reasonable explanation and expectation that the participant may have become eligible (at the discretion of the investigator) post discussion with the Clinical Trial Leader or designee. For rescreening, the participant must re-consent to participation in the trial, all screening examinations must be repeated, and a new participant number assigned.

Potential reasons for rescreening could be:

- Positive urine drug screen
- Restricted medications like CYP sensitive drugs/alternative or traditional medicine
- Clinically significant findings per the investigator's judgement
- Initiation of hormonal contraceptive

6.2.1.2 Retesting

Participants with unexpected lab values at Visit 1 may be retested once within the 30-day screening period if there is a reasonable explanation and expectation that the participant will meet the in- and exclusion criteria during the retest at the discretion of the investigator. This doesn't apply to the urine drug screen, which must not be retested.

6.2.1.3 Demographics

During the screening visit, demographic information will be collected. This includes:

- Age (in years) on the day of informed consent
- Sex (male or female, in order to describe the trial participant's sex at birth)

- Gender identity (male, female, non-binary, not answered, or other in order to describe how the trial participant self-identifies, regardless of their genotypic or phenotypic sex) if 1) locally accepted (i.e. based on HA/EC/IRB acceptance, independent of acceptance by investigators or participants), 2) investigators are willing to ask, and 3) participants are willing to reply
- For women of childbearing potential, yes/no in order to characterise the participant population and as a basis for contraception requirements
- Ethnicity and race in order to sufficiently characterise the participant population, to support possible subgroup analyses if needed, and to support the calculation of the kidney function via the CKD EPI formula unless not acceptable according to local regulations

